**Official Title: Physical Therapy and Deep Brain Stimulation in Parkinson Disease**

**NCT Number: NCT03181282**

**Document Date: May 11, 2017**

## **I. Specific Aims**

The purpose of this study is to examine the safety, feasibility, and preliminary efficacy of PT in people with PD with STN-DBS. We expect that participants with STN-DBS in the PT group will not report more adverse effects than those in the control group. Furthermore, we hypothesize that those in the PT group will complete at least 80% of prescribed PT sessions. We also expect that those in the PT group will demonstrate improvements in balance and gait while those in the control group will demonstrate no change or a decline in balance and gait.

Specific Aim 1: To determine the safety of an 8-week PT intervention in people with STN-DBS. The primary variable of interest for safety is the number of adverse events (e.g. falls, orthopedic injuries).

Hypothesis 1: We hypothesize that participants with STN-DBS plus PT will not report more adverse effects than those with STN-DBS only.

Specific Aim 2: To determine the feasibility of an 8-week PT intervention in people with STN-DBS. The primary variable of interest for feasibility is adherence to the PT intervention, measured as a percentage of PT sessions completed.

Hypothesis 2: We hypothesize that participants with STN-DBS will complete at least 80% of prescribed PT sessions.

Specific Aim 3A: To evaluate the preliminary efficacy of PT on balance in people with STN-DBS. The primary variable of interest is the Balance Evaluation Systems Test (BESTest) total score.

Hypothesis 3A: We hypothesize that participants with STN-DBS plus PT will demonstrate improvements in balance while those with STN-DBS only will demonstrate no change or a decline in balance.

Specific Aim 3B: To determine the preliminary efficacy of PT on gait in people with STN-DBS. The primary variables of interest is preferred-pace gait velocity.

Hypothesis 3B: We hypothesize that participants with STN-DBS plus PT will demonstrate improvements in preferred-pace gait velocity while those with STN-DBS only will demonstrate no change or a decline in gait.

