Physical therapy, delivered using various treatment approaches (e.g. treadmill training, balance training), is effective in reducing postural instability and improving spatiotemporal gait characteristics among individuals with PD who do not have DBS. To our knowledge, there are no studies to date that assessed the impact of PT for those with PD who have DBS. In fact, the current standard of care following STN-DBS does not include PT. Current care post-DBS includes pharmacologic management and monitoring of DBS settings, which are optimized based on Unified Parkinson’s Disease Rating Scale motor subsection (UPDRS III) scores. Despite the introduction of substantial changes to neural activity in areas of the brain governing movement with DBS, formal movement training or assessment of functional mobility and safety are not provided after surgery. As such, patients may not experience significant improvements in postural stability and gait following surgery, and may be at increased risk for falls, fall-related complications, and development of a sedentary lifestyle. Physical therapy is a personalized intervention that can be used to address specific movement impairments that remain even when patients are on optimal regimens of medication and DBS. There is an urgent need to determine if PT is effective in improving postural stability and gait performance over time following STN-DBS. If the intervention is safe and feasible, future studies could evaluate the efficacy of PT for gait and balance deficits in this population before and/or immediately post-surgery, increasing the potential impact of this research.

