### **Interim Monitoring and Early Stopping**

Safety will be monitored throughout the study. If it is noted that the physical therapy intervention is unsafe (i.e. more than 2 falls across multiple individuals are occurring within the intervention sessions), the research team will meet to determine whether or not it is safe to continue. We will not conduct an interim data analysis to determine whether the study should continue.

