### **Statistical Analysis Plan**

The total number of adverse events will be reported for each group allowing for qualitative comparisons.

Adherence will be reported for both attendance of PT and control sessions and will be expressed as percent of sessions completed.

Balance and gait data will be analyzed using mixed models with repeated measures or appropriate non-parametric test as appropriate to test for main effects of group (PT, control) and time (baseline, 8-weeks) and group\*time interactions ( $\alpha \leq 0.05$ ).

If there are baseline differences in demographic variables (e.g. age, gender, years since PD diagnosis, years since DBS), we will use these variables as covariates in the analyses.

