### **Power**

To our knowledge, there are no intervention studies that specifically examined the efficacy of physical therapy on balance in people with PD with STN-DBS. Given that this is a pilot study, the authors chose an effect size that would be meaningful and required to support moving forward with a larger trial. As such, with a medium effect size of 0.25 (Cohen's  $f$ ) and an alpha level of 0.05, 14 participants per group will provide 82% power to detect significant differences between or within groups for the primary preliminary efficacy outcome (i.e., BESTest). Factoring in a potential for 20% dropout attrition rate based on prior studies, we plan to recruit 17 participants per group. This pilot study is not powered to detect significant differences in the number of adverse events between groups.

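### Aim 1 sets out to determine the safety of PT from a qualitative comparison of adverse-event totals, with no interval to show how large an excess 14 to 17 participants per arm leaves open

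*Combined protocol and SAP*

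**What the plan says.** Safety is the first aim in section I, Specific Aims: "To determine the safety of an 8-week PT intervention in people with STN-DBS". The variable is the number of adverse events, and the only stated expectation is Hypothesis 1: "We hypothesize that participants with STN-DBS plus PT will not report more adverse effects than those with STN-DBS only".

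The Statistical Analysis Plan section gives adverse events one sentence: "The total number of adverse events will be reported for each group allowing for qualitative comparisons". The Power section adds: "This pilot study is not powered to detect significant differences in the number of adverse events between groups". That section plans 14 participants per group for analysis and 17 per group recruited.

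Interim Monitoring and Early Stopping has a separate trigger: the team meets if "more than 2 falls across multiple individuals are occurring within the intervention sessions". The trigger makes no comparison with control. Section II, Background and Significance, looks ahead: "If the intervention is safe and feasible, future studies could evaluate the efficacy of PT for gait and balance deficits".

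The documents give no margin, confidence interval, upper bound or expected rate for adverse events.

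**The concern.** The aim is worded as a determination, and the hypothesis as an absence of excess. In a small sample, seeing no excess is weak evidence that there is none. The Power section's disclosure warns against expecting a significant difference. It does not tell the reader how large a true excess would fit the data if the two totals came out similar.

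What is at stake is the safety sentence in the report. If it says that PT was safe, or caused no more adverse events than control, readers planning later studies may take that as settled when the data are also compatible with a material excess of falls or injuries. Choosing a different count to tabulate, such as participants affected, would not change this.

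**Working it through.** **Inputs from the documents.** 14 participants per arm analysed and 17 recruited (Power); 1:1 allocation (Randomization Method). There is no stated adverse-event figure to reproduce: the 82% power in the Power section concerns the BESTest only.

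**Assumed inputs.** Mean events per control participant mu = 0.1 to 2. Counts are either Poisson or over-dispersed (gamma-Poisson with shape k = 0.5 or 1, so per-person variance mu + mu²/k). Arm totals are then Poisson with mean n·mu, or negative binomial with mean n·mu and shape n·k.

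**Step 1. Hypothesis 1 read literally, as PT total ≤ control total.** This reading is an illustration, not a rule in the plan. If PT has no effect, the expectation is missed with probability (1 − P(tie))/2. With n = 14, mu = 0.1 and Poisson counts, P(tie) = 0.253, giving (1 − 0.253)/2 = 0.374. With n = 17, mu = 2 and k = 0.5, P(tie) = 0.023, giving (1 − 0.023)/2 = 0.489. When PT multiplies the rate, P(PT total ≤ control total) is summed exactly over both distributions. Each range below spans n = 14 and 17, Poisson and both over-dispersed cases.

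| Events per control participant | No effect: missed | 1.5-fold rate: met | Doubled rate: met |
|---|---|---|---|
| 0.1 | 37–39% | 44–48% | 30–36% |
| 0.25 | 42–44% | 31–38% | 14–25% |
| 0.5 | 45–46% | 21–32% | 5–19% |
| 1 | 46–48% | 11–28% | 1–15% |
| 2 | 47–49% | 4–26% | 0–13% |

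Overall, a harmless PT misses the expectation 37–49% of the time. A 1.5-fold rate meets it 4–48% of the time, and a doubled rate 0–36%. The high ends belong to rare events. The low ends belong to frequent Poisson events, where a doubling would almost always show.

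**Step 2. What identical observed rates leave open.** The approximate upper limit of the two-sided 95% interval for the rate ratio, when the observed ratio is 1, is exp(1.96·√(2/(n·mu) + 2/(n·k))). The second term is absent for Poisson counts.

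- Poisson, n = 17, mu = 2: exp(1.96·√(2/34)) = 1.61.
- Poisson, n = 14, mu = 0.5: exp(1.96·√(2/7)) = 2.85.
- Over-dispersed, n = 17, mu = 2, k = 1: exp(1.96·√(2/34 + 2/17)) = 2.28.
- Over-dispersed, n = 14, mu = 0.5, k = 0.5: exp(1.96·√(2/7 + 2/7)) = 4.40.

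So at 0.5 to 2 events per person the limit is 1.6 to 2.9 (Poisson) or 2.3 to 4.4 (over-dispersed). It is wider for rarer events: the exact conditional Poisson limit is 5.4 at 4 v 4 events. That method gives 3.3 at 7 v 7, where the approximation gives 2.85, so the approximation is if anything optimistic.

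**Step 3. Serious events.** With none observed in the PT arm, the one-sided 95% upper bound on the proportion affected is 1 − 0.05^(1/n): 0.193 for n = 14 and 0.162 for n = 17.

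**The case against.** The strongest reply is that this is a pilot that describes adverse events, says openly that it cannot test them, and draws no formal conclusion. Much of that stands, and it rules out three stronger readings.

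- A reader might infer that PT will be declared safe if its total is no higher than control's, and unsafe otherwise. The plan contains no such rule. Hypothesis 1 states an expectation and the comparison is qualitative, so Step 1 describes only a literal reading.
- A reader might infer that safety will rest on a non-significant test, and then calculate how often such a test misses harm. No adverse-event test is planned. The 0.05 level in the Statistical Analysis Plan section is attached to balance and gait.
- A reader might treat Background and Significance as a formal gate to later trials. Its wording is permissive and is not tied to Hypothesis 1.

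The plan also has other safeguards: weekly adverse-event tracking in both arms, reporting of serious events to the IRB, and the in-session falls trigger. These protect participants, but none of them says how large an excess over control the comparison leaves open.

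It is also fair to say that an interval does not supply a margin. Formal non-inferiority on the proportion with any event would need 36 to 99 per arm for an assumed 20-point margin (one-sided 0.025, 80% power, equal true risks of 10% to 50%). That is out of reach here, which is a reason to estimate rather than conclude.

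**Conclusion.** The point holds as a minor one. The wording of Aim 1 and Hypothesis 1 promises more than a qualitative comparison of totals in 14 to 17 per arm can deliver, and the plan provides nothing that would show the reader the remaining uncertainty. The disclosed lack of power lowers the severity but does not fill that gap.

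The 16–19% bound for serious events needs only the sample size and an observed count of zero. Every other figure depends on assumed event rates and dispersion. An excess of two-fold or more is not left open in every scenario: with frequent Poisson events the limit falls to 1.6.

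**What to change.** In the Statistical Analysis Plan section, keep the counts and add two items:

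- the PT/control adverse-event rate ratio (or rate difference) with a 95% confidence interval that allows for over-dispersion;
- the exact upper 95% bound for serious adverse events in the PT arm.

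In Specific Aims, reword Aim 1 and Hypothesis 1 as estimating the adverse-event rate with PT and the largest excess over control compatible with the data. Pre-state the reporting sentence, for example: *no safety signal seen; an excess of up to [upper limit] is not excluded*. Use it in place of a statement that PT is safe or causes no more events than control.

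The cost is wording in two sections and one interval estimate from forms already completed weekly in both arms. No participants, visits or staff are added. The downside is a less favourable safety statement, because the interval will be wide.

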## **II. Background and Significance**

Subthalamic nucleus deep brain stimulation (STN-DBS) effectively reduces tremor, rigidity, and bradykinesia in people with Parkinson disease (PD), but the effects of STN-DBS on postural instability and gait are less clear. Postural stability initially improves following STN-DBS; however, these benefits may not endure. For example, worsened postural responses were observed in individuals six months post-DBS surgery, and STN-DBS did not improve balance in individuals with PD with abnormal quiet stance prior to surgery.

## Physical Therapy and Deep Brain Stimulation in Parkinson Disease (PTDBS)

Further, despite positive initial effects of STN-DBS on postural instability and gait difficulty (PIGD), PIGD progressively worsened and within two years was more impaired than before surgery. Finally, falls may increase after STN-DBS surgery. With respect to gait, STN-DBS is effective in improving spatial parameters (e.g. stride length), but does not seem to change temporal parameters. Stride-to-stride variability, known to be impaired in PD, was unchanged following STN-DBS. More importantly, approximately 42% of individuals post-STN-DBS subjectively reported worsened gait when on medication.

Deficits in balance and gait may lead to falls, fall-related complications, and physical inactivity in people with PD. These negative effects are thought to lead to a ‘malignant’ form of PD in which there is reduced quality of life and increased risk for mortality. While people who have had STN-DBS often experience reductions in tremor, rigidity, and bradykinesia, surgical management of PD may not be effective in ameliorating impairments in balance and gait. In fact, investigators have reported that DBS may worsen balance, which may accelerate an individual’s decline toward ‘malignant’ PD. To this end, recent studies indicate physical activity levels did not increase after STN-DBS. This finding should not go unnoticed as physical activity may have a disease modifying effect, slowing the progression of motor disability. As of 2011, approximately 70,000 people with PD have undergone DBS, with the annual number of DBS procedures for PD totaling between 8,000-10,000^18. In addition, investigators are now studying the effects of STN-DBS in people with early PD. The procedure appears to be safe and effective in this population, which will increase the number of surgical candidates. With the number of people with PD expected to double to more than 8 million by 2030^22, the number of those receiving DBS is expected to substantially increase.

Given the expected rise in STN-DBS procedures and potential for worsening of postural instability and gait deficits, there is a clear need for interventions that prevent these negative complications of STN-DBS.

Physical therapy, delivered using various treatment approaches (e.g. treadmill training, balance training), is effective in reducing postural instability and improving spatiotemporal gait characteristics among individuals with PD who do not have DBS. To our knowledge, there are no studies to date that assessed the impact of PT for those with PD who have DBS. In fact, the current standard of care following STN-DBS does not include PT. Current care post-DBS includes pharmacologic management and monitoring of DBS settings, which are optimized based on Unified Parkinson’s Disease Rating Scale motor subsection (UPDRS III) scores. Despite the introduction of substantial changes to neural activity in areas of the brain governing movement with DBS, formal movement training or assessment of functional mobility and safety are not provided after surgery. As such, patients may not experience significant improvements in postural stability and gait following surgery, and may be at increased risk for falls, fall-related complications, and development of a sedentary lifestyle. Physical therapy is a personalized intervention that can be used to address specific movement impairments that remain even when patients are on optimal regimens of medication and DBS. There is an urgent need to determine if PT is effective in improving postural stability and gait performance over time following STN-DBS. If the intervention is safe and feasible, future studies could evaluate the efficacy of PT for gait and balance deficits in this population before and/or immediately post-surgery, increasing the potential impact of this research.

## Physical Therapy and Deep Brain Stimulation in Parkinson Disease (PTDBS)

### III. Methods

#### Participants

Participants will be recruited from the community.

**Inclusion Criteria:** Participants with PD will be  $\geq 30$  years of age and have a neurological diagnosis of PD. PD diagnostic criteria include those used for clinically defined “definite PD”, as previously described by Racette et al. based upon established criteria. Each must have had clear benefit from levodopa and meet the other inclusionary and exclusionary criteria below.

All participants will meet the following inclusion criteria:

- 1) At least one year post-surgery for STN-DBS for PD
- 2) No evidence of dementia (MMSE  $\geq 24$ ).

**Exclusion Criteria:**

- 1) Serious medical problem (aside from PD)
- 2) History or evidence of other neurological deficits, such as previous stroke or muscle disease
- 3) History or evidence of orthopedic, muscular, or psychological problem that prevents participation in either intervention
- 4) Inability to walk 10 meters with or without assistive device

#### Measures

**Adverse Events:** Adverse events will be measured using a questionnaire administered on a weekly basis.

**Feasibility of PT:** Feasibility of PT sessions will be measured by the number of sessions attended relative to the total possible number of sessions (i.e., 16).

#### **Preliminary Efficacy:**

**Balance:** To assess balance, each participant will complete the Balance Evaluation Systems Test (BESTest). This is a 27-item assessment that requires the participant to complete a variety of balance tasks like standing on one leg, walking with changes in speed, and standing on foam with eyes closed. The total possible score ranges from 0-100% with higher scores indicated better balance.

**Gait:** To assess gait, participants will walk at their preferred pace across a GAITRite walkway, which will determine their gait velocity in centimeters per second. Higher gait velocities are associated with better walking ability.

#### Protocol

A phone screen will be used to screen study candidates for eligibility. All eligible participants will be scheduled to start the study as soon as they are able at a time that is convenient to both the participant and the research team.

## Physical Therapy and Deep Brain Stimulation in Parkinson Disease (PTDBS)

### **Baseline Testing**

Baseline testing will be conducted with participants in two conditions: 1) OFF stimulation / OFF medication, 2) ON stimulation / ON medication. These conditions will be tested on two separate days within one week of each other and the order of conditions will be randomized. The OFF stimulation / OFF medication and ON stimulation / ON medication testing sessions will occur on two separate days to avoid fatigue. Regardless of testing condition, upon arriving for the first laboratory visit, informed consent will be obtained from each participant.

**Informed Consent and MMSE:** Participants will be consented in a private room with only the participant and study team members present. Participants will first receive a verbal explanation of the study and then be given as much time as they wish to read the consent form and ask any questions they may have. Participants will provide written informed consent prior to commencing study participation.

The Mini-Mental Status Examination (MMSE) will be conducted first only in the ON stimulation / ON medication condition. If the participant scores less than 24/30, the participant will be excluded from further participation at this time. If the score is 24 or above, the baseline assessment will proceed. After completing the MMSE in the ON stimulation / ON medication condition, each participant will complete the battery of balance, walking, and motor function tests.

For the OFF stimulation / OFF medication condition, participants will arrive to the laboratory in the practically defined off-state of their medication cycle (i.e.  $\geq 12$  hours since last dose). The deep brain stimulators will be turned off and the participant will then wait 45 minutes until the physical assessment begins. After 45 minutes, each participant will complete a battery of balance, walking, and motor function tests.

Upon completion of the baseline visits, the participant will be randomized to either the intervention or control group.

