### **Safety and Adverse Events**

The research team will do everything possible to ensure safety of all participants over the course of this study. Potential adverse events related to this study may include falls with serious injury, major cardiovascular incidents, or serious injuries associated with physical activity. The Adverse Event tracking form will be completed weekly with every participant. The adverse event most likely to occur in this study is a participant fall due to walking. Members of the research team will all be trained in fall prevention and will closely monitor all participants throughout all aspects of the study in case of a need to assist with balance to prevent a fall. In the case of a serious adverse event, emergency medical care will be sought immediately if needed. Any serious adverse events will be reported to the local IRB in accordance with their policies and procedures.

These risks will be addressed in the following ways:

- a) Effects of withholding overnight and morning anti-PD medications: Participants may experience a temporary worsening of your Parkinson's disease symptoms as a result of not taking their anti-Parkinson's medication for study evaluations. Once taking the medication, the symptoms should return to their typical levels. Effects of medication withdrawal will be monitored and if the effects are too severe, participants will immediately take their medication. At that point, the study will be discontinued.
- b) Effects of turning off deep brain stimulators: Participants may experience a temporary worsening of your Parkinson's disease symptoms as a result of turning off the deep brain stimulators for study evaluations. Once we turn the stimulators on, the symptoms should return to their typical levels. Effects of stimulation withdrawal will be monitored and if the effects are too severe, participants will immediately have their stimulators turned on. At that point, the study will be discontinued.

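### Participants randomised to OFF/OFF first go at least 12 hours without anti-PD medication for the study before they sign consent

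*Combined protocol and SAP*

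**What the plan says.** All of the sequence is in the combined protocol and SAP.

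- **Before the first visit (Protocol).** Candidates are screened for eligibility by phone and then scheduled. No consent step is described here.
- **Order of baseline days (Baseline Testing).** OFF/OFF and ON/ON are tested on separate days, and "the order of conditions will be randomized". The allocation ratio is not given.
- **Timing of consent (Baseline Testing).** "Regardless of testing condition, upon arriving for the first laboratory visit, informed consent will be obtained from each participant". The paragraph on informed consent adds the setting: "Participants will be consented in a private room with only the participant and study team members present". It also gives the general rule: "Participants will provide written informed consent prior to commencing study participation".
- **State on arrival for OFF/OFF (Baseline Testing).** "participants will arrive to the laboratory in the practically defined off-state of their medication cycle", defined as 12 hours or more since the last dose. The stimulators are turned off after arrival, followed by a 45-minute wait.
- **Risk list (Safety and Adverse Events, item a).** The item is headed "Effects of withholding overnight and morning anti-PD medications". It attributes possible temporary worsening of symptoms to omitting medication for the study's evaluations.

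**The concern.** For an OFF-first participant, the rule on when consent is taken and the rule on medication state at arrival cannot both be followed without the missed doses coming before the signature. The problem arises when the plan is carried out exactly as written, not from a deviation.

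What is at stake is participant protection. The protocol itself names this withholding as a risk of taking part, and a person should agree in writing before taking on a named study risk. These participants also read and sign the form while off medication, whereas ON-first participants sign while on it.

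**Working it through.** The plan gives no figure on this point. The check is to put the stated steps in time order, then count who is affected.

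**Step 1: order of events by assigned first day.** Let arrival at the first visit be time 0.

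| Event | ON/ON first | OFF/OFF first |
|---|---|---|
| Phone screen and scheduling | before 0 | before 0 |
| Last anti-PD dose | as usual | 12 hours or more before 0 |
| Written consent | at 0 | at 0 |
| Stimulators off for testing | at the second visit | after consent, at the first visit |
| Withholding for the OFF/OFF day | after consent | before consent |

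Only the right-hand column is out of order. There the gap between last dose and signature is at least 12 hours. Part of that gap may coincide with a normal night, but the risk item refers to overnight and morning doses being withheld, so doses due before arrival are missed for the study.

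**Step 2: is the withholding part of the study?** Three statements bear on this:

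1. Written consent precedes participation ("Participants will provide written informed consent prior to commencing study participation").
2. Written consent is obtained on arrival at the first visit, whichever state is tested.
3. Omitting medication is done for the study's evaluations and is a listed study risk.

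For OFF-first participants, statements 1 and 2 agree only if the withholding in statement 3 is not participation. No section says so, and the risk list points the other way.

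**Step 3: is an exception made elsewhere?** The opening words of the consent rule cover both states explicitly, so OFF-first participants are not exempt. The verbal explanation, reading time and questions are described together with the private-room consent. The consent discussion that the text describes therefore also follows the withholding.

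**Step 4: number affected.** The Power section plans 17 per group.

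- Planned total: 17 × 2 = 34.
- Order ratio 1:1 (assumed): 34 × 1/2 = 17 OFF-first.
- Range if the OFF-first to ON-first ratio lay between 1:2 and 2:1 (assumed): 34 × 1/3 = 11.3 to 34 × 2/3 = 22.7.

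Anyone who attends an OFF/OFF first visit but is never assigned to a group would add to this. The documents give no rate for that, so it is not estimated.

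**Step 5: does it reach the analysis?** The Baseline Testing and Randomization Method sections reveal group assignment only after both baseline visits. Consent timing therefore cannot differ systematically between PT and control, and nothing in the Statistical Analysis Plan or Power sections depends on it.

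**The case against.** The strongest reply is that the protocol already states the right principle, that written consent comes first, and never defines the moment at which participation begins. If missing doses at home is regarded as preparation, no rule is broken. The consent pages are not in the supplied text and the content of the phone screen is not given, so candidates may have been told about the withholding and agreed to it verbally. A participant who arrives off medication must have had some instruction beforehand. The period before consent is also milder than the full OFF/OFF state, because stimulation continues until the laboratory, and the protocol describes the worsening as temporary.

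Much of this stands, and it limits the point to written consent and to medication. It does not remove the point. The body of the protocol fixes when and where written consent is taken, and a verbal agreement would not meet the protocol's own requirement for a written one.

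A reader might infer more than the documents support:

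- *That participants withhold medication uninformed.* Prior explanation by phone cannot be excluded.
- *That stimulation is also withdrawn before consent.* It is turned off in the laboratory, after arrival.
- *That consent signed in the off-medication state is invalid.* The documents say nothing about capacity in that state.
- *That unsupervised hours at home strengthen the case.* The same hours recur before the 8- and 12-week OFF/OFF visits, well after consent, so they are a separate matter that changing consent timing would not resolve.
- *That the late MMSE exposes ineligible people to the OFF/OFF session.* The phone screen may already have removed them, and the number could be zero.

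**Conclusion.** The point holds as a defect in the order of procedures. As Baseline Testing is written, OFF-first participants take on a listed study risk before they give written consent, and they sign while off medication. This conflicts with the written-consent rule in the same section.

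The conclusion rests on reading study-directed withholding as participation, which the risk list supports, and on there being no earlier written consent step, since none appears in the supplied text. The size, about half of those planned, rests on an assumed 1:1 order ratio.

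This matters for participant protection and for the consistency of the protocol. It is not a source of bias, and a reader should not discount the balance or gait results because of it. It is worth correcting because the text states a sequence that is wrong, rather than merely omitting detail, and the correction is small.

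**What to change.** Amend Baseline Testing to say that signed written consent is obtained before a participant is asked to withhold any anti-PD medication for the study. Participants whose first day is OFF/OFF would sign remotely, or at an earlier contact arranged around the existing phone screen. ON-first participants can continue to sign on arrival. If consent is remote, adjust the sentence that places consent in a private room with study team members. The randomised order and the follow-up visits stay as they are.

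The cost is one short extra consent contact for each OFF-first participant, about 17 people under the 1:1 assumption, plus a brief amendment.

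Holding ON/ON first for everyone would also work and needs no extra contact, but it gives up the randomised order. It is acceptable only if the sponsor does not need state order counterbalanced. The Statistical Analysis Plan tests group, time and their interaction and plans no ON-versus-OFF comparison, but the sponsor may want the order for other reasons. If this route is taken, the same order should be used at 8 and 12 weeks so that any order effect is common to all time points.
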